1.1 TABLE OF EVENTS

	Screening Period	Enrollment	Treatment period							End of Treatment	Follow-up Visit
			2	3	4	5	6	7	8		
Visit	0	1	2	3	4	5	6	7	8	9	
Week	up to 4 wks	0	2	4	8	12	16	20	24	28	
Day (Visit Window)	-1 to -28	1	14 (± 4)	28 (± 4)	56 (± 4)	84 (± 4)	112 (± 4)	140 (± 4)	168 (± 4)	196 (± 4)	
Determination of eligibility	X	X									
Review of medical history	X	X									
Obtain informed consent	X										
Randomization		X									
Study drug dispensing		X	X	X	X	X	X				
Managing drug accountability			X	X	X	X	X	X	X	X	
Vital signs	X	X	X	X	X	X	X	X	X	X	
Physical exam	X	X		X	X	X	X	X	X	X	
Serum hCG (if applicable)	X										
Urine hCG (if applicable)		X		X	X	X	X	X	X	X	
Hematology panel	X	X	X	X	X	X	X	X	X	X	
Comprehensive metabolic panel	X	X	X	X	X	X	X	X	X	X	
Lipid panel		X		X	X	X	X	X	X	X	
Glycosylated hemoglobin	X	X		X	X	X	X	X	X	X	
HOMA-IR	X	X		X	X	X	X	X	X	X	
Urinalysis	X					X				X	
Electrocardiogram	X					X				X	
Liver biopsy (if prior biopsy > 12 mo)	X										
PK study		X*			X		X		X		
Review concomitant meds	X	X	X	X	X	X	X	X	X	X	
Review adverse events **		X**	X	X	X	X**	X	X	X**	X	
MRI for hepatic steatosis	X					X				X	
CK-18		X				X				X	
Stored serum for exploratory measures and noninvasive biomarkers of fibrosis		X				X				X	
Exit Interview											X

* Frequent sampling PK study on Day 1 for Substudy subjects only. All patients to have a pre-dose trough level drug measures (6 ml blood) at treatment Weeks 8, 16, and 24 (Visits 4, 6, and 8).

** Hospital Anxiety and Depression Scale and Columbia Suicide Severity Scale

2. ABBREVIATIONS AND DEFINITIONS OF TERMS

AE	Adverse event
ALD	Alcoholic liver disease
ALT	Alanine aminotransferase
AST	Aspartate aminotransferase
BUN	Blood urea nitrogen
CFR	Code of Federal Regulations
CK-18	Cytokeratin 18
CRF	Case report form
CRO	Contract research organization
CTCAE	Common terminology criteria for adverse events
EC	Ethics committee
EKG	Electrocardiogram
FDA	Food and Drug Administration
GCP	Good Clinical Practice
GGT	Gamma-glutamyl transferase
β-HCG	β-human chorionic gonadotropin
HBsAg	Hepatitis B surface antigen
HCV	Hepatitis C virus
HIV	Human immunodeficiency virus
HSC	Hepatic stellate cells
HOMA-IR	Homeostatic Model Assessment of Insulin Resistance
IB	Investigator's brochure
ICF	Informed consent form
ICH	International Conference on Harmonization of Technical Requirements for Registration of Pharmaceuticals for Human Use
IDRB	Independent Data Review Board
IL	Interleukin
IND	Investigational new drug
INR	International normalized ratio
IRB	Institutional Review Board
ITT	Intent-to-treat
KO	Knock-out
LDH	Lactate dehydrogenase
LPS	Lipopolysaccharide
MedDRA	Medical dictionary for regulatory activities
MCD	Methionine choline deficient
MCP-1	Monocyte chemotactic protein 1
MMP-1	Matrix metallopeptidase 2
MRI	Magnetic resonance imaging
NAFLD	Nonalcoholic fatty liver disease
NASH	Nonalcoholic steatohepatitis
NASH CRN	Nonalcoholic Steatohepatitis Clinical Research Network
NCI	National Cancer Institute

NFK- β	Nuclear factor-kappa beta
SAE	Serious adverse event
TNF- α	Tumor necrosis factor alpha
TLR-4	Toll like receptor 4
TIR	Toll/IL-1 receptor
TLR	Toll-Like Receptors
TTR	Time to remission

3.0 BACKGROUND

3.1 *Nonalcoholic Steatohepatitis (NASH)*

The emerging epidemic of obesity and metabolic syndrome has contributed to the increased prevalence of nonalcoholic steatohepatitis (NASH) as what is now considered to be the leading cause of chronic liver disease in the Western World [1]. An estimated 25% of the industrialized world has hepatic steatosis and fatty liver, an entity that has been termed nonalcoholic fatty liver disease (NAFLD). NAFLD encompasses a spectrum of liver pathology with different clinical prognoses. The simple accumulation of triglyceride within hepatocytes (hepatic steatosis) is on the most clinically-benign extreme of the spectrum. On the opposite, most clinically-ominous extreme, are cirrhosis and primary liver cancer. The risk of developing cirrhosis is extremely low in individuals with chronic hepatic steatosis, but increases as steatosis becomes complicated by histologically-conspicuous hepatocyte death and inflammation, i.e., nonalcoholic steatohepatitis (NASH). NASH affects approximately 20-25% of all NAFLD patient, which equates approximately 6.0% of the overall population [2]. NASH resembles alcoholic liver disease but occurs in people who drink little or no alcohol [3].

Most subjects with NAFLD are asymptomatic. The diagnosis is often made when abnormal liver aminotransferases or features of fatty liver are noted during an evaluation performed for other reasons. NAFLD may also be diagnosed during the work-up of vague right upper quadrant abdominal pain, hepatomegaly, or an abnormal appearing liver at time of abdominal surgery. The association of NAFLD with obesity, diabetes, hypertriglyceridemia, hypertension, and cardiovascular disease is well known. NAFLD is an independent risk factor for metabolic syndrome and type 2 diabetes mellitus [4]. In addition, approximately 50-90% of patients with obesity may have NAFLD while 50% of patients with diabetes may have biopsy proven NASH and are at increased risk for progressive hepatic fibrosis and cirrhosis [5, 6].

The mechanisms underlying NAFLD pathogenesis and progression are not entirely clear. The best-understood mechanisms pertain to hepatic steatosis. Hepatic steatosis results when hepatocyte mechanisms for triglyceride synthesis (e.g., lipid uptake and *de novo* lipogenesis) overwhelm mechanisms for triglyceride disposal (e.g., degradative metabolism and lipoprotein export), leading to accumulation of fat (i.e., triglyceride) within hepatocytes. Obesity stimulates hepatocyte triglyceride accumulation by altering the intestinal microbiota to enhance both energy harvest from dietary sources and intestinal permeability. Reduced intestinal barrier function increases hepatic exposure to gut-derived products which stimulate liver cells to generate inflammatory mediators that inhibit insulin action and cause oxidative or inflammatory stress. Increased delivery of triglyceride precursors (e.g., fatty acids and diacylglycerols) and metabolic by-products (e.g., reactive oxygen species) may damage hepatocytes, leading to hepatocyte lipotoxicity. Lipotoxicity also triggers the generation of other factors (e.g., inflammatory cytokines, hormonal mediators) that deregulate systems that normally maintain hepatocyte viability and result in progressive chronic liver injury.

Weight reduction with diet and exercise is the only therapeutic strategy that has been shown to be beneficial in NASH. Unfortunately, most patients are unable to achieve and maintain the required lifestyle change for any significant period of time. Bariatric surgery is effective for

weight loss, but has not been specifically assessed as a treatment for NASH and may be contraindicated in those patients with advanced liver disease attributable to NAFLD. Insulin sensitizing agents such as metformin and glitazones have been used experimentally with some limited evidence of short term benefit; however, the benefits are not sustained. Experimental approaches under clinical evaluation in patients with NASH include antioxidants, newer antidiabetic medications and antifibrotic agents. In two pilot trials, pentoxifylline [7, 8], which inhibits Tumor necrosis factor alpha (TNF- α) production, was reported to show beneficial effects in improving aminotransferase levels, hepatic steatosis, fibrosis and necroinflammation among patients with NASH. *Currently, there are no FDA-approved treatments for NAFLD and NASH.*

3.2 Toll-Like Receptor 4

Toll-like receptor 4 (TLR-4) is a cell surface, type 1 trans-membrane protein that recognizes bacterial lipopolysaccharides (LPS) and endotoxins, among other ligands, a key mediator of the release of proinflammatory cytokines and inflammatory responses, and a member of TLR family which are mainstays of the innate immune system and best known for their role in host defenses against infections. Lipopolysaccharide (LPS), an endotoxin, is a specific agonist for TLR-4. Activation of inflammatory signaling pathways is of central importance in the pathogenesis of alcoholic liver disease (ALD) and NASH. Recent studies demonstrated that Toll-like receptors, the sensors of microbial and endogenous danger signals, are expressed and activated in innate immune cells as well as in parenchymal liver cells involved in hepatic fibrosis (hepatic stellate cells and Kupffer cells) and thereby contribute to ALD and NASH [9]. The importance of gut-derived endotoxin and its recognition by TLR4 in the liver, the significance of TLR-induced intracellular signaling pathways and cytokine production as well as the contribution of TLR-4 signaling to the induction of liver fibrosis and to the progression of liver pathology suggest that a TLR-4 antagonist for therapeutic target for the treatment of chronic liver disease [10].

3.3 Obesity, Insulin resistance and TLR-4

Chronic low-grade inflammation is a hallmark of obesity and thought to contribute to the development of obesity-related insulin resistance. TLR-4 is a key mediator of pro-inflammatory responses. Mice lacking TLR-4s are protected from diet-induced insulin resistance and inflammation. Mice deficient in hepatocyte TLR-4 (TLT4KO) exhibit improved glucose tolerance, enhanced insulin sensitivity and ameliorated hepatic steatosis despite the development of obesity after a high-fat diet (HFD) challenge [11]. Furthermore, TLR4KO mice have reduced macrophage content in white adipose tissue, as well as decreased tissue and circulating inflammatory markers. TLR4 are activated by fatty acids and endotoxinemia (a marker of gut permeability), features of both obesity and metabolic syndrome, resulting in activation of nuclear factor-kappa beta (NFK- β) and increased release of inflammatory biomediators such as IL-6, IL-1, TNF- α , and monocyte chemotactic protein-1 (MCP-1), which play a role in the pathophysiology of obesity and metabolic syndrome [12]

Such data indicate that the activation of TLR-4 on hepatocytes contributes to obesity-associated inflammation and insulin resistance, and suggest that targeting hepatocyte TLR-4 might be a useful therapeutic strategy for the treatment of type 2 diabetes [13]. Given the very strong

association of metabolic syndrome and obesity in that pathogenesis of NAFLD and NASH, targeting TLRs can potentially forestall the end-organ complication of insulin resistance syndrome, including the development obesity-related chronic liver disease.

3.4 Endotoxemia, LPS and NASH

Emerging data have shown a close association between compositional changes in gut microbiota and the development of NAFLD [14, 15]. The change in gut microbiota may alter nutritional absorption and storage. In addition, gut microbiota are a source of TLR ligands, and their compositional change can also increase the amount of TLR ligands delivered to the liver. TLR ligands can stimulate liver cells to produce proinflammatory cytokines. Therefore, the gut-liver axis has attracted much interest, particularly regarding the pathogenesis of NAFLD [16]. The abundance of the major gut microbiota, including Firmicutes and Bacteroidetes, has been considered a potential underlying mechanism of obesity and NAFLD, but the role of these microbiota in NAFLD remains unknown [17]. Several reports have demonstrated that certain gut microbes are associated with the development of obesity and NAFLD. For instance, a decrease in Akkermansia muciniphila causes a thinner intestinal mucus layer and promotes gut permeability, which allows the leakage of bacterial components. Interventions to increase Akkermansia muciniphila improve the metabolic parameters in obesity and NAFLD. In children, the levels of Escherichia were significantly increased in NASH compared with those in obese control. Escherichia can produce ethanol, which promotes gut permeability [18]. Another possibility by which the altered intestinal microbiota may promote obesity and fatty liver is an increase in LPS-containing microbiota [19] and increased intestinal permeability to LPS [20]. Bacterial LPS stimulates Kupffer cells and participates in the pathogenesis of hepatic fibrogenesis [21]. Thus, normalization of gut microbiota using probiotics or prebiotics is a promising treatment option for NAFLD. In addition, TLR signaling in the liver is activated, and its downstream molecules, such as proinflammatory cytokines, are increased in NAFLD. To date, TLR2, TLR4, TLR5, and TLR9 have been shown to be associated with the pathogenesis of NAFLD. Therefore, gut microbiota and TLRs are targets for NAFLD treatment. Thus, plausible evidence exists to support the use of a TLR-4 antagonist in the treatment of NASH.

3.5 JKB-121

JKB-121, a methylenemorphinandiol compound, is a long-acting small molecule that is efficacious as a weak antagonist at the TLR-4 receptor, thus reducing the likelihood of affecting the innate immune system. It is an off-patent FDA-approved drug (as a non-selective opioid antagonist) with no known safety issues.

JKB-121 has been shown to prevent the LPS induced inflammatory liver injury in a methionine/choline deficient (MCD) diet fed rat model of NAFLD [22]. In vitro, JKB-121 neutralized or reduced the LPS-induced release of IL-6 and IL-12 in murine macrophages, deactivated hepatic stellate cells (HSCs), inhibited HSCs proliferation, collagen expression and α -SMA expression in cultured HSCs (spontaneously activated) [23]. In vivo, JKB-121 neutralized the stimulated release of TNF- α , IL-6, and IL-18 by LPS/D-Gal in mice. Moreover, JKB-121 also neutralized LPS-induced p38 phosphorylation and TNF- α in isolated rat Kupffer cells [22]. The data supports that JKB-121, a TLR4 antagonist, exhibits the potential for treating

NASH. Based on the evidence reviewed above, inhibition of the TLR4 signaling pathway may provide an effective therapy in the prevention of inflammatory hepatic injury in NAFLD, the progression to NASH and fibrosis, and ultimately cirrhosis.

4. STUDY CONDUCT STATEMENT

This study will be conducted in compliance with the protocol, according to current United States federal regulations (21, Code of Federal Regulations [CFR] Parts 50, 56 and 312D) and the principles of International Conference on Harmonization (ICH) (ICH E6 1997) Good Clinical Practice (GCP), Food and Drug Administration (FDA) guidelines and the Declaration of Helsinki.

5. STUDY OBJECTIVES AND ENDPOINTS

5.1 Objectives

5.1.1 Primary Objective

To evaluate the safety and potential efficacy of two dose levels of JKB-121 (5 mg twice daily and 10 mg twice daily) in reducing liver fat compared to placebo.

5.1.2 Secondary Objective(s)

The secondary objectives are:

- Determine the pharmacokinetic profile of JKB-121 in NASH
- Assess the impact of treatment with JKB-121 on metabolic markers
- Assess the impact of treatment on liver enzymes (serum ALT) over 24 weeks.
- Establish the recommended dose for future NASH treatment studies.
- To evaluate changes of NASH related biomarkers such as adiponectin, leptin, ghrelin, TNF-alpha, TGF-beta, hyaluronic acid and MMP-2.

5.1.3 Exploratory Object(s)

Investigate the impact of treatment of potentially relevant inflammatory and metabolic biomarkers associated with NASH.

5.2 Endpoints

5.2.1 Primary Endpoint

The primary endpoint of this study is safety and potential efficacy of two dose levels of JKB-121 (5 mg twice daily and 10 mg twice daily) in reducing liver fat compared to placebo.

5.2.2 Secondary Endpoint(s)

The secondary endpoint of the study is time to remission (TTR). TTR is defined as time in weeks from randomization to liver function remission as defined as two consecutive ALT values within normal range (< 20 U/mL for woman and < 30 U/L for men) or 20% reduction from the baseline during study period.

- TTR rate in ALT at the end of the treatment period.
- Assess the pharmacokinetic profile of JKB-121 in NASH

- Change on metabolic markers associated with NASH
- Change in liver enzymes (serum ALT) over 24 weeks.
- Change of NASH related biomarkers such as adiponectin, leptin, ghrelin, TNF-alpha, TGF-beta, hyaluronic acid and MMP-2.

6. STUDY DESIGN

This is a randomized, double-blind, placebo controlled, parallel-group, phase II trial of JKB-121 in treating subjects with biopsy-proven NASH.

[figure not shown]
Subjects will be randomized at study entry to placebo twice daily, 5 mg twice daily, or 10 mg twice daily of JKB-121 orally to improve NASH with regard to biochemical and MRI/MRS features of NASH in a 1:1:1 ratio.

- Treatment Group 1: placebo twice a day orally
- Treatment Group 2: 5mg of JKB-121 twice a day orally
- Treatment Group 3: 10 mg of JKB-121 twice a day orally

The maximum time on study drug for each subject is 24 weeks with an additional 4 weeks of follow-up.

This allocation is shown diagrammatically in Figure 1

Figure 1: Study Schema

6.1 Duration of the Study

Subjects will be on treatment for up to 24 weeks. Subjects who experience adverse reaction will discontinue study drug but will continue to complete all protocol-specified follow-up visits, assessments and evaluations. They will then continue to be followed up for the remaining duration of the study. Unless otherwise recommended by the Independent Data Review Board (IDRB) or regulatory authorities, the study will continue until it accrues a minimum of 60 subjects complete the study.

Until formal conclusion of the study, subjects, investigators and all site study personnel will be remain blinded as to treatment allocation, except in the event of a medical emergency which necessitates unblinding.

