6.3 Reasons for Subject Withdrawal

Any subject may withdraw his or her consent at any time.

Subjects will be monitored carefully during the study. Any subject who experiences an increase in ALT value greater than 3X baseline during the treatment period will be monitored weekly. If ALT values increase to greater than 5X the baseline ALT will be rechecked within 48 hours and if value remains $>$ 5X baseline, the subject will be withdrawn from the study. The subject will then be followed, and ALT, AST, prothrombin time, and total bilirubin will be monitored every 2 weeks thereafter until the value that led to the subject's discontinuation of therapy has returned to the baseline value (Baseline for prothrombin time and total bilirubin is the value obtained at the screening).

Other reasons for withdrawal from the study may include, but are not limited to the following:

- Subject is in violation of the protocol, defined as refusal or inability to adhere to prescribed dosing and/or follow-up regimen.
- Subject is lost to follow-up.
- Subject experiences a serious or intolerable AE that, in the medical opinion of the principal investigator, warrants discontinuation.
- Subject has laboratory safety assessments that reveal clinically significant worsening from baseline values.
- Subject develops, during the course of the study, symptoms or conditions listed in the exclusion criteria.
- Subject requires a medication that is prohibited by the protocol.
- Investigator or TaiwanJ Pharmaceuticals requests an early discontinuation of the trial for any reason.

The investigator may also withdraw a subject upon the request of TaiwanJ Pharmaceuticals or if TaiwanJ Pharmaceuticals terminates the study. Upon occurrence of a serious or intolerable AE, the principal investigator will confer with TaiwanJ Pharmaceuticals. If a subject is discontinued because of an AE, the event will be followed until it is resolved or until the principal investigator or sub-investigator deems the event to be chronic or the subject to be stable.

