10. SCHEDULE OF EVENTS

10.1 Tests and Evaluations

No subject may be permitted to undergo any protocol-specified investigations or interventions in this study until they have provided a signed, dated, written informed consent.

All tests and evaluations must be performed prior to that day's administration of study drug treatment. Subjects should undergo all tests and evaluations specified in the protocol, regardless of whether they remain on study drug. Insofar as possible, all blood samples should be collected at approximately the same time of day in each visit, in order to minimize diurnal variation.

The required procedures for patient evaluation at each study visit are outlined in the study. Schedule of Visits and Procedures are in Sections 10.2 and detail items in section 10.3 through 10.4.8. Detailed instructions for specific procedures are presented in Section 11.

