10.4.4 End of Treatment Visit 8 (week 24 ± 4 days)

Subjects must be in a fasted state for at least 8 hours prior to sample collection at these visits, which is a requirement for some of the blood tests that will be performed as noted below. If a subject has discontinued treatment, every attempt should be made to have the subject return to the site and complete the procedures / assessments that are required at the End of Treatment Visit (Week 24) and the Follow-up Visit (Week 28). The following will be performed for all subjects who meet the inclusion criteria and not of the exclusion criteria

- Verify the study drug was administered correctly
- Document drug accountability and any problems with drug administration in the source documents.
- Record vital signs
- Physical examination
- Record weight
- Electrocardiogram
- Urinalysis
- Hospital Anxiety and Depression Scale and Columbia Suicide Severity Scale
- Complete blood samples for:
 1. Complete blood count with differential
 2. Blood chemistry including: ALT, AST, albumin, alkaline phosphatase, bicarbonate, BUN, calcium, chloride, creatinine, glucose, LDH, magnesium, phosphorus, potassium, sodium, total and direct bilirubin, protein, uric acid, and GGT/
 3. Fasting glucose and insulin level for HOMA-IR
 4. Lipid panel
 5. Glycosylated hemoglobin
 6. Urine pregnancy test (only for women of childbearing potential).
 7. Serum and plasma samples for non-invasive biomarkers related to liver injury pathophysiology and/or TLR-4 pathway
 8. ELF test—Subjects must be in a fasted state prior to the sample collection
 9. FibroSURE/ FibroMAX/ FibroTest—Subject must be in a fasted state prior to the sample collection
 10. Additional blood sample needs to be collected for pharmacokinetic study
- Counsel subjects on weight loss, diet and exercise
- MRI for quantification of hepatic fat
- Record any adverse events occurring after signing of the informed consent form
- Record all medications that the subject has taken since prior visit

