12.4 Toxicity Management Guidelines

The toxicity management will be based on DAIDS AE Grading system,

Hepatic toxicity:

ALL patients will have increased liver enzymes at baseline. Liver function tests will be monitored with each visit. For any elevated ALT 5-10.0 X ULN (Grade 3 or 4) on study drug, repeat testing and evaluation will be performed in 1 week. Treatment will be interrupted for drug-related Grade 3 AE until their AE Grade is less than 3. Liver function tests and assessment will be performed weekly to ensure resolution of Grade 3 AE. Study drug may be resumed following confirmation of resolution of Grade 3 AE or if investigator confirms AE is keeping with patient's underlying NASH. The investigator must assess whether or not Grade 3 AE is clinically or not clinically significant in the setting of NASH and in reference to baseline ALT levels. Increases in liver enzymes $> 3 \times$ subject's baseline will prompt retesting and patient examination within 1 week. Increases in liver enzymes $> 5 \times$ subject's baseline will prompt immediate drug discontinuation and withdrawal from study. For non-drug related Grade 3 AE, Investigator will perform further clinical management based on subject's clinical condition and/or other biochemistry results.

DAIDS Grading	Lab Value						INR	Clinical management	
	ALT *		AST		Bilirubin (total)			Non Drug Related	Drug Related
Grade 1	1.25-2.5 x ULN	and/or	1.25-2.5 x ULN	and/or	1.1-1.5 x ULN	and/or	1.2-1.3	Non treatment modification	
Grade 2	2.6-5.0 x ULN	and/or	2.6-5.0 x ULN	and/or	1.6-2.5 x ULN	and/or	1.4-1.5	Non treatment modification	
Grade 3	5.1-10.0 x ULN	and/or	5.1-10.0 x ULN	and/or	2.6-5.0 X ULN	and/or	1.5-2.0	Further clinical management will be judged by Investigator	Treatment interruption may be suggested by Investigator
Grade 4	$> 10.0 \times$ ULN	and/or	$> 10.0 \times$ ULN	and/or	$> 5.0 \times$ ULN	and/or	> 2.0	Treatment termination and withdraw	

* Subjects with elevated ALT > 10.0 ULN will be withdrawn from this study.

Discontinuation of treatment should be considered if:

- ALT or AST $> 10 \times$ ULN
- ALT or AST $> 5 \times$ ULN for more than 2 weeks
- ALT or AST $> 3 \times$ ULN and total bilirubin $> 2 \times$ ULN or INR > 1.5
- ALT or AST $> 3 \times$ ULN with the appearance of fatigue, nausea, vomiting, right upper quadrant abdominal pain, fever, rash or eosinophilia ($> 5\%$).

Other toxicities

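### Protocol 6.1 and 10.1 keep subjects who stop drug on every visit, but 6.3 and 12.4 withdraw hepatic-toxicity subjects from the study, leaving the Week 24 MRI to best effort and the interim visits unsecured

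*Protocol*

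**What the plan says.** **General rule.** Protocol 6.1 says that subjects with an adverse reaction "will discontinue study drug but will continue to complete all protocol-specified follow-up visits, assessments and evaluations". Protocol 10.1 adds: "Subjects should undergo all tests and evaluations specified in the protocol, regardless of whether they remain on study drug".

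**Hepatic rule.** Under Protocol 6.3, if ALT is still above 5x baseline on a recheck within 48 hours, "the subject will be withdrawn from the study". Protocol 12.4 says that liver enzymes above 5x baseline "will prompt immediate drug discontinuation and withdrawal from study". The Grade 4 row of its table reads "Treatment termination and withdraw", and the footnote reads "Subjects with elevated ALT > 10.0 ULN will be withdrawn from this study".

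**What follows a hepatic withdrawal.**
- 6.3 requires ALT, AST, prothrombin time and bilirubin every 2 weeks until recovery. It states this for the ALT trigger above 5x baseline.
- 12.4 has adverse events followed to resolution or stability, and 12.3.1 has SAEs reported to 30 days after the last dose.
- 6.3.1 seeks the Visit 8 and Visit 9 assessments where that can be done.
- 10.4.4 says: "If a subject has discontinued treatment, every attempt should be made to have the subject return to the site" for the Week 24 and Week 28 procedures. Its list includes "MRI for quantification of hepatic fat" and the recording of adverse events. 10.4.5 repeats the request.
- 10.4.6 instead describes an End of Treatment visit, if possible, and one visit 4 weeks later. The synopsis (Study duration) gives 28 days of follow-up after stopping drug.

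**Other permanent stops.** Confirmed malignancy (10.6) and emergency unblinding (12.5.1) end study drug, but the subject is asked to stay in the study.

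**The concern.** A subject with a severe on-treatment liver-test rise falls under both rules, and no text says which governs. The specific hepatic rule takes the subject off the schedule for a reason that may be related to treatment. The primary endpoint is the change in MRI liver fat at Week 24 in all dosed subjects, so a lost off-drug MRI is potentially informative missing data. Withdrawn subjects are not replaced (6.3.2), and the sample size makes no allowance for dropout (SAP 6.1).

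SAP 6.9.1 would impute a missing MRI from treatment, diabetes stratum and the available MRI values. ALT, which triggers the withdrawal, is not in that model. A subject withdrawn before Week 12 with no return visit has no scheduled post-baseline MRI to impute from.

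The handling of an MRI taken at early withdrawal is also open. Protocol 6.3.1 calls the assessments Visit 8, so SAP 6.2 could use the scan as Week 24 by its label. The synopsis groups early-withdrawal visits with unscheduled ones, so SAP 6.2 could window it instead.

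**Working it through.** **1. The rules side by side**

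| Event | Drug | Later schedule |
|---|---|---|
| Adverse reaction (6.1); any drug status (10.1) | Stopped under 6.1 | All visits and assessments |
| Malignancy (10.6); emergency unblinding (12.5.1) | Stopped permanently | Asked to remain in the study |
| Confirmed ALT >5x baseline (6.3) | Stopped | Withdrawn; liver tests every 2 weeks |
| Liver enzymes >5x baseline (12.4) | Stopped at once | Withdrawn |
| ALT >10x ULN or other Grade 4 liver value (12.4) | Terminated | Withdrawn |

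The hepatic action rules also disagree with each other. 6.3 acts after a recheck, whereas 12.4 acts at once. For ALT or AST above 10x ULN, 10.4.7 and the closing list of 12.4 make stopping drug optional or something to consider, whereas the Grade 4 row is mandatory, as is the footnote for ALT.

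**2. Scheduled visits at stake** (visit table: Weeks 4, 8, 12, 16, 20, 24, 28)

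Visits left under 6.1 and 10.1: after a stop at Week 4, six; at Week 12, four; at Week 20, two.

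- Upper bound: the End of Treatment visit takes place at the stop, with one visit 4 weeks later. This timing is an assumption; only 10.8, on withdrawal of consent, states it. One visit is kept.
- Lower bound: the Week 24 and Week 28 return visits both succeed (10.4.4, 10.4.5). Two visits are kept.

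| Stop | Lost, upper bound | Lost, lower bound |
|---|---|---|
| Week 4 | 5/6 = 83% | 4/6 = 67% |
| Week 12 | 3/4 = 75% | 2/4 = 50% |
| Week 20 | 1/2 = 50% | 0/2 = 0% |

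At the upper bound the true Week 24 MRI is lost each time. At the lower bound it is kept, and only a stop before Week 12 loses an MRI, the one at Week 12. The counts exclude the two-weekly liver tests.

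**3. Effect on the primary comparison**

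The documents give no rate of hepatic withdrawal, so k and d are assumptions. Let k of 20 subjects in an arm have an imputed Week 24 change that is off by d percentage points on average.

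- If the endpoint is the Week 24 value, the arm mean shifts by k × d / 20: 1 × 2 / 20 = 0.1; 1 × 5 / 20 = 0.25; 2 × 5 / 20 = 0.5.
- SAP 6.9.1 Step 3 averages Weeks 12 and 24. If Week 12 was observed, the error per subject halves and the shift is k × d / 40: 1 × 2 / 40 = 0.05; 2 × 5 / 40 = 0.25.

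The range is therefore about 0.05 to 0.5 points, against a planned effect of about 5% (read as points).

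**4. Scale check on power**

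The stated 85% power for 5 points with 20 per arm gives no SD. Solving back with a t-test gives an SD of about 5.1. With that SD, losing 1 or 2 Week 24 MRIs per arm lowers complete-case power from 85% to about 83% or 81%.

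**5. Windows for an early MRI under SAP 6.2**

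If the halfway rule uses all scheduled visits, Week 24 runs from (140 + 168)/2 = Day 154 to (168 + 196)/2 = Day 182. If it uses MRI visits only, the lower limit is (84 + 168)/2 = Day 126. The SAP does not say which.

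**The case against.** The strongest reply is that 6.1 and 10.1 are general, 6.3 and 12.4 are specific, and sites would normally apply the specific rule. On that view divergence between sites is conjecture. This largely stands: divergence is possible but not shown. It does not help the data, because consistent use of the specific rule is what removes the scheduled visits.

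A second reply is that 10.4.4 already asks for every effort to obtain the Week 24 MRI, and that no protocol can compel attendance. This stands for the Week 24 MRI, where the gain from a change is modest. It does not cover the interim visits or the Week 12 MRI. The text also competes with 10.4.6 and the synopsis 28-day rule.

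A reader might infer that safety follow-up ends at a hepatic withdrawal. The documents do not support that. Liver tests and event follow-up continue, SAEs are reported for 30 days, and the Visit 8 and Visit 9 lists record new adverse events. What is not assured is adverse-event recording between the stop and any return visit, since section 12 ends it at premature withdrawal. The tables would change little, because SAP 6.11.1 does not count events that start more than 7 days after the last dose as treatment-emergent.

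Finally, the trial calls its objectives exploratory. That limits the weight of the point but does not remove the contradiction.

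**Conclusion.** The contradiction is real and worth correcting. Hepatic toxicity leads to mandatory study withdrawal, while the general rule and the other permanent stops keep subjects in the study. The Week 24 and Week 28 visits are then best-effort, and the interim visits are not secured. The same holds for the Week 12 MRI after an early stop.

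The size is modest and uncertain. The number of subjects affected may be zero, and the direction of any bias is unknown. The shift of 0.05 to 0.5 points rests on assumed values (k = 1 to 2 per arm, d = 2 to 5 points); the lower end applies if Step 3 averages an observed Week 12 value with the imputed one. A reader might go further and conclude that the Week 24 MRI is always lost or that the primary result is materially biased. The text of 10.4.4 contradicts the first, and nothing in the documents establishes the second.

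**What to change.** **Protocol.**
- In 6.3 (the ALT rule and the bullet on serious or intolerable adverse events) and in 12.4 (text, Grade 4 row, footnote), replace withdrawal from the study with permanent discontinuation of study drug. The subject stays on all scheduled visits and MRIs through Weeks 24 and 28 unless he or she declines. The wording of 12.5.1 can be reused.
- In the same edit, state one action rule for ALT above 5x baseline, saying whether the 48-hour recheck applies.
- State one rule for ALT or AST above 10x ULN, mandatory or optional, and bring 10.4.7 and the closing list of 12.4 into line with it.
- Limit 10.4.6 and the synopsis 28-day rule to subjects who decline further visits.

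**SAP 6.2.** Assign an early-termination MRI by actual study day, not by visit label, and state the Week 24 window in days. Day 154 to 182 fits if the halfway rule uses all scheduled visits; the lower limit is Day 126 if it uses MRI visits only.

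**Cost.** A protocol amendment with IRB/IEC approval at about 12 sites, and a short SAP addition. No visit is added beyond those 6.1 and 10.1 already require, and subjects still come off drug for hepatic toxicity. Some subjects will attend visits off drug.
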